2.1.2 Involvement of neurotensin in cancer growth

In an excellent review, Carraway et al[6] describe the pathways that seem to play a role in NT-induced cancer cell growth. NT interacts with NT receptor (NTSR) to activate a set of protein kinase C (PKC) isotypes that may specify which paths the signal undertakes. This additionally relies on the level of expression for the effectors implicated. Path 1: cell surface shedding of EGFlike ligands via the action of metalloprotease(s) activates EGFR, which employs a variety of kinase cascades made known to support nuclear transcription and cell cycle control. The effect of PKC could be both causal (via path 1) and permissive (via path 2). Path 2: direct activation of Raf-1 by PKC can also take place independent of EGFR. Path 3: by stimulating storeoperated Ca2+-channels, NT triggers phospholipase A2 (PLA2) and diacylglyserol (DAG) lipase to release arachidonic acid, which is changed to lipoxygenase (LOX) products. This additionally enhances the activation of growth-regulatory PKCs. Path 4: NT can raise cAMP levels in cancer cells, which is considered to involve a superactivation of adenylyl cyclase (AC). This result necessitates a background of Gs activity, seemingly from another G protein-coupled receptor (GPCR) coupled to Gs. Commonly, the result is growth inhibition via PKA-mediated effects on Raf-1. However, in cases where B-Raf levels are high, growth augmentation occurs via effects on

mitogen-activated protein (Mek).

Even though NTS1 expression might amplify gradually through the inflammation-carcinogenesis-loss of barrier and enhancement sequence, Carraway et al[6] hypothesize that NT signaling is augmented mainly by upregulation of its signaling partners [EGFR, ERK (extracellular signalregulated kinase), Akt (Protein kinase B) and LOX] and possibly by an increased release of NT in response to fat. The sequence of signaling partner expression undeniably differs for various cancers.

Muller et al [26] propose that neurotensin stimulates phosphorylation of ERK and Akt is mediated by diverse pathways: in HCT116 cells, neurotensininduced DNA synthesis and phosphorylation of ERK is mediated mainly by PKC separately to EGFR transactivation. In addition, neurotensin provokes phosphorylation of Akt via activation of metalloproteinases, succeeding detachment of ligands that activate the EGFR.

Maoret et al [14] found that NT stimulated growth of five different human cancer lines (SW480, SW620, HT29, HCT116, C1.19A) shown to express NTSR1, whereas it had no effect on caco-2 cells shown to lack NTSR1. In SW480 cells, NT enhanced proliferation by two- to three-fold and increased colony formation by approximately 50%.

Gui et al [15] showed that NTSR1 expression enhancement is gradual through neoplastic transformation of colonic epithelium. In the normal colon, NTSR1 expression was principally confined to basal cells in the deep portion of the crypts, a compartment known to include the self-renewing epithelial stem cell population.[27] Quite the opposite, NTSR1 expression was weak to absent in superficial epithelial cells, suggesting that NTSR1 may be a factor in

supporting the growth of self-renewing cells, and that downregulation of the receptor may be necessary during terminal differentiation in the normal colonic epithelium. In addition, NTSR1 expression was generally higher in the deep advancing margins and invasion sites than in the rest of the tumor. Souaze et al [28] claim that the upregulation of NTSR1 in colon cancer is mainly assigned to activation of the Wnt/APC signaling pathway. Modifications in Wnt/APC take place frequently at the early premalignant stage, and are seen as critical to the progression of colon cancer. Activation of the NTSR1 gene was achieved by agents that triggered b-catenin buildup, as well as a drop in endogenous NTSR1 when the tumor suppressor gene APC was restored to cancer cells.

2.1.3 Neurotensin-Mediated Interleukin-8

The signaling pathways and transcription factors regulating IL-8 expression have been described in different cell types in response to various stimuli.[29] Resembling other physiologic agents, neurotensin takes effect through Ca2+/PKC, ERK activation and the ubiquitous AP-1 and NF-kB transcription factors to provoke IL-8 gene expression in HCT116 cells. Most studies have revealed that NF-kB plays the principal role in IL-8 regulation. Wang et al. found that both ERK-dependent AP-1 and ERK-independent NF-kB activation was necessary for neurotensin-mediated IL-8 mRNA and secretion in HCT116 cells.[30]

2.1.4 Low levels of neurotensin

Low plasma neurotensin values in colorectal cancer group can be partially explained by the internalization of the peptide. A model emerges providing G protein-coupled receptors (GPCR) endocytosis, implicated in a number of

intracellular signaling mechanisms like the MAP kinases pathway.[31] When internalized, the ligand-receptor complex is targeted to early endosomes, and the receptor is then either recycled to the cell surface or addressed to lysosomes for degradation. Neurotensin receptors [NTSR1, NTSR2, and Sortilin1 (SORT1] competently internalize the peptide. The involvement of accessory proteins like dynamin, amphiphysin and intersectin in the internalization of NTSR1 has been studied in different cell expression systems.[32] Interestingly, overexpression of intersectin, a scaffold protein, inhibits the efficiency of NTSR1 sequestration in COS-7 cells but not in HEK293 cells, suggesting cell-type specific pathways of NT endocytosis via NTSR1.[32] Neurotensin receptors can act individually, or in combination in certain tissues or organs. A complex formed between the NTSR1 and the SORT1 is able to internalize NT in HT29 cells.[33] Metabolic clearance of the peptide in addition to inactivation at sites of action is probable, given the low levels of intact NT mirrored by high levels of NT fragments in the systemic circulation. [34, 35] According to these data, a future study on tissue expression vs. circulating NT level is justified.

3. STUDY DESIGN ASPECTS

We consider sending Participant Information Sheet (PIS) about the present study to patients due to have colonoscopy via regular mail along with their appointment letter. Research Nurses are already available on both sides will inform and consent patients for blood sampling. We consider let all participants know about the analysis of results of this study. A letter will be

sent with the main findings and the potential implications for the future of the bowel cancer screening.

Blood sample will be Centrifuged and serum will be kept frozen at -80°C in both hospital sites until it will be transferred to the Biomedical and Life Sciences, Lancaster University for ELISA measurement.

Each Participant will be explained the objectives of the study, will sign the consent form for participation and will be cannulated for colonoscopy (the vast majority of patients undergoing colonoscopy wish to have sedation/analgesia) and blood will be drawn from the cannula before the administration of the sedation/analgesia for their colonoscopy.

Two of the investigators ([name] and [name] will be involved in participants colonoscopy.

Participant data or samples will be identified by the unique study number. Participants will not be referred to a separate research team and the arrangements for identification and referral will be kept strictly to the participating trusts. The aforementioned information will be explained clearly in the letter of invitation and/ or written information for participants. In the occasional case that we will recruit prisoners, their GP will receive all the necessary information.

The initial approach to potential participants should be made by a member of the healthcare team responsible for patients' colonoscopy as it is normally done in the endoscopy unit. The research Nurse will be present as well in order to inform and consent patient for the taking of the blood sample. The identification of potential participants will not involve reviewing or screening the identifiable personal information. Research will entail the taking

participant blood, measurement of biomarkers and statistical analysis to document their predictive value. There will not be any direct or indirect clinical implication to participant health care management.

Blood samples sent to the Faculty of Health and Medicine in Lancaster University will be identified by the Hospital Number and the NHS Number. Data will be inserted in Hospital (FGH, RPH) based computer database. Resources for participants' data will be GP referrals to Hospital outpatient clinics and Hospital Electronic Patient Records. Responsible for the aforementioned arrangements will be the principal investigator: [name], Consultant General Surgeon.

Data storage will be in hospital and university-based computers. Data base transfers from the two participating trusts to the University of Lancaster and vice-versa will be performed with military encryption USB sticks provided by the trusts.

Research data after the study has ended will be stored in the network of University Hospitals of Morecambe Bay. Confidential information (including personal data) will be destroyed and disposed of securely once it is no longer required, after periods of retention have expired, or in cases where destruction is required for legal or ethical reasons, in accordance with the Lancaster University's Information Handling Policy. Sensitive paper documents will be shredded, and electronic data will be securely erased. We will seek assistance from our IT Services for advice on the secure disposal of electronic data.

3.1 CONTROL(S) / COMPARATOR(S)

All individuals fulfilling the inclusion criteria will be enrolled. After the refinement of participants by the exclusion criteria blood sample will be drawn for Neurotensin and IL-8. Following the report of colonoscopy and the histology individuals will be assigned in three groups: a) group A - cancer patients, b) group B – adenoma (polyp) patients and c) group C – No pathology/normal colonoscopy. Two primary analyses will be conducted to define the cut-off plasma values for Neurotensin and IL-8 for a) diagnosing cancer (group A versus group C) and b) diagnosing adenomas (group B versus group C). A secondary analysis will be conducted comparing the performance of the Neurotensin/IL-8 system towards the 2-weeks referral and FOB test positive patients for the diagnosis of colorectal cancer and adenomas.

The reason for using participants without bowel pathology is because we need to define the "normal range" of Neurotensin and IL-8 serum values.

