2. INTRODUCTION

Cancer research offers a better insight into regulatory mechanisms involved in cell proliferation in colorectal cancer, and might eventually guide us to new possibilities in terms of novel biomarkers that would facilitate early diagnosis.

Neurotensin (NT) mediates its effects by binding to three neurotensin receptors NTSR-1, -2, and -3: the first two are G-protein coupled receptors, whereas the third belongs to the sortilin receptor superfamily. [6-8] NT via NTSR-1 initiates a multiplicity of intracellular signaling pathways in colon cancer cells and in non-transformed NCM460 colonocytes, as well as the epidermal growth factor receptor (EGFR) and downstream mitogenactivated protein kinases (MAPK) via the metalloproteinase-dependent cleavage of pro- TGF alpha.[9] NT-mediated activation of MAPK signaling and the downstream transcription factor activator protein 1 (AP1) also occurs rapidly in human colorectal cell lines.[10] Moreover, transactivation of the IL-8 promoter is triggered by NT-mediated AP1 activation [10, 11] while NT also stimulates Ras pathway and nuclear factor kappa-light-chain-enhancer of activated B cells (NF-kB) -dependent secretion of IL-8.[6, 12] Intense transcription of the NTSR-1 gene via TCF/Lef- and nuclear β-catenindependent pathways can explain NTSR-1 overexpression in colon cancer.[13] Higher NT levels are also obtained from colon cancers compared to normal colon tissues, and in vivo evidence establishes that NT/NTSR-1 signaling is fundamental for tumor growth.[14]

Gui et al [15] found that NTSR1 expression was considerably increased in both adenomas and adenocarcinomas compared with histologically normal epithelium and in adenocarcinomas compared with adenomas.

Given that colorectal cancer is the second leading cause of cancer-related death in Europe and the third in the USA, a new non-invasive screening modality with the potential for high population compliance at a lower cost than the current screening system and with the capacity for early detection of

colorectal cancer and precursor adenomatous polyps is of paramount importance.[16, 17]

This pilot study aims to investigate whether specific pattern of serum neurotensin/NTSR1/IL-8 values can detect patients with adenomas or colorectal cancer and determine the feasibility of these agents being used as a screening tool.

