3.3 OUTCOME MEASURES

The primary endpoints are firstly the cut-off of the serum Neurotensin and IL-8 values selected by the ROC curves and the demonstrated estimate of area under ROC curve (accuracy) in predicting colorectal cancer and colorectal adenomas.

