3.5 PROPOSED SAMPLE SIZE / POWER CALCULATIONS

Assuming that the AUC of the new test is commensurate with the pilot study (AUC=0.85), we calculate the number of samples required to obtain a 95%

confidence interval of size 0.1. We assume that the ROC curve follows a binormal distribution, and that the prevalence of adenoma/cancer is between 20-30% in the study participants. We obtain that we require between 400 (30% prevalence) and 553 (20% prevalence) participants. We therefore target an enrollment of 500 patients. We intend to perform an interim analysis after 50% of the patients have been included and evaluated.

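### Group B is labelled adenoma (polyp), so patients with only non-adenomatous or unexamined polyps fit no other stated group and can be counted as adenoma cases in a primary analysis

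*Protocol*

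**What the plan says.** Protocol section 3.1 sets the allocation: "Following the report of colonoscopy and the histology individuals will be assigned in three groups". After cancer as group A come "group B – adenoma (polyp) patients" and "group C – No pathology/normal colonoscopy". The same section gives two primary analyses, and the second is for "diagnosing adenomas (group B versus group C". It adds that participants without bowel pathology are used because they define the normal range of the markers.

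Section 3.3 makes the ROC-selected cut-offs primary, together with the "area under ROC curve (accuracy) in predicting colorectal cancer and colorectal adenomas". The introduction (section 2) names the lesion of interest: early detection of "colorectal cancer and precursor adenomatous polyps is of paramount importance".

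The exclusion criteria in section 3.2 remove, among others, inflammatory bowel disease, inherited colorectal cancer and cancer at another site. They do not remove patients with non-adenomatous polyps. No section says which histological result places a patient in B, or what happens to a polyp that has no histology.

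**The concern.** The target condition of the second primary analysis is adenoma, but the label of its case group treats adenoma and polyp as one category. Not every polyp is an adenoma: hyperplastic and inflammatory polyps are not. A patient with only such a polyp has to go somewhere, and the three groups leave one place.

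The case definition is the reference standard of a diagnostic accuracy study, so this is not a detail to be settled later. If non-adenomas sit among the adenoma cases and their markers look like those of controls, the B-versus-C AUC is pulled towards 0.5 and the selected cut-off may move. A weak adenoma result could then reflect the case definition and not the markers. The number of adenoma cases would also be overstated. Recruiting more patients would not correct this, because it is a bias and not imprecision.

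**Working it through.** **Step 1. Where can the patient go?** Take a patient whose only finding is a non-adenomatous polyp, and apply section 3.1.

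- Group A needs cancer: no.
- Group C needs no pathology and a normal colonoscopy: no, a polyp was found.
- Group B is labelled adenoma, with polyp in brackets: fits on the bracketed word, does not fit on the first word.
- Exclusion under section 3.2: none applies.

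B is therefore the only stated group that can take this patient. The same holds for a polyp without histology.

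**Step 2. The plan's own precision figure.** Section 3.5 starts from "Assuming that the AUC of the new test is commensurate with the pilot study (AUC=0.85", a binormal ROC curve, a 95% confidence interval of total width 0.1 (half-width 0.05), and an adenoma/cancer prevalence of 20% to 30%. It reports 400 participants at 30% and 553 at 20%. With the binormal variance of Obuchowski:

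- a = 1.414 × z(0.85)
- V = 0.0099 × exp(−a²/2) × [(5a² + 8) + (a² + 8)/k], with k = (1 − prevalence)/prevalence
- cases = 1.96² × V / 0.05², and N = cases × (1 + k)

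At 30% prevalence this gives 120.0 cases and N = 400.0. At 20% it gives 110.6 cases and N = 552.9. Both stated figures reproduce. They do not depend on how group B is defined, so they neither support nor refute the point. They do give a benchmark, the half-width of 0.05.

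**Step 3. Effect of non-adenomas in group B.** Let f be the share of group B with only non-adenomatous polyps, and assume that their markers are distributed as in group C. A comparison of such a patient with a control then has AUC 0.5, so

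observed AUC = (1 − f) × AUC + f × 0.5, a fall of f × (AUC − 0.5).

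The protocol does not give f, so the range is an assumption. It gives no adenoma AUC either, so two values are shown.

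| f | True AUC 0.85: observed (fall) | True AUC 0.75: observed (fall) |
|---|---|---|
| 10% | 0.815 (0.035) | 0.725 (0.025) |
| 20% | 0.780 (0.070) | 0.700 (0.050) |
| 30% | 0.745 (0.105) | 0.675 (0.075) |

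The fall passes 0.05 when f exceeds 0.05/0.35 = 14% at an AUC of 0.85, and when f exceeds 0.05/0.25 = 20% at 0.75.

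**Step 4. Limits of the benchmark.** The half-width of 0.05 was planned with adenoma and cancer pooled as cases. With the cancers taken out, B versus C has fewer cases, and at the same AUC and total N its interval will be wider. The comparison with 0.05 is therefore a guide to scale only.

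**The case against.** The strongest reply is that the bracketed word is only a lay gloss. The sentence bases allocation on histology as well as the colonoscopy report, its first word is adenoma, the analysis statements in sections 3.1, 3.3, 4.1 and 4.2 refer to adenomas, and the introduction writes of adenomatous polyps. Histology would serve little purpose for group B if any polyp qualified. This stands in part. A reader might infer that the plan definitely counts every polyp patient as an adenoma case, and the document does not support that, because the text is ambiguous. But the gloss reading still leaves the non-adenomatous polyp with no group, and no histological criterion for B is written down. Staff at the two sites could resolve this differently.

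The second reply is that dilution is assumed. This stands. It needs a material share of such patients in B and control-like serum markers, and the protocol gives neither. Section 2.1.1 reports that in the pilot neurotensin separated controls from all the other disease groups, which are not listed, and section 2.1 discusses IL-8 in an inflammatory context. Control-like values cannot be presumed, least of all for inflammatory polyps. The protocol's tissue evidence of NTSR1 rising with neoplastic change gives no reason to expect a marker change in non-neoplastic polyps, but it concerns receptor expression and not the serum levels measured here.

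The third reply is that 0.85 is the wrong starting point. This also stands: in section 2.1.1 it is the pilot neurotensin AUC for cancer. A lower adenoma AUC gives a smaller fall, which is why 0.75 is shown as well.

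A patient with both cancer and an adenoma is a lesser matter. The natural reading puts that patient in A, and one clause settles it.

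**Conclusion.** The point holds as a defect in the case definition: as labelled, the three groups allow patients with only non-adenomatous or unexamined polyps to be counted as adenoma cases in one of the two primary analyses. The size of the effect is conditional. With control-like markers and f of 10% to 30%, the B-versus-C AUC falls by 0.035 to 0.105 from 0.85, or by 0.025 to 0.075 from 0.75. If these polyps resemble adenomas in their markers, there is little or no dilution. The possible shift in the cut-off cannot be sized from the document.

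It would go too far to conclude that the adenoma AUC is diluted, or that the bias exceeds the planned precision. Both depend on a share and on marker values that the protocol does not contain. The change is still worth making, because a primary endpoint is exposed and the correction is cheap.

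**What to change.** In section 3.1, delete the bracketed word and define group B as patients with at least one histologically confirmed adenoma and no cancer. State that cancer together with adenoma is assigned to A.

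Keep patients with only non-adenomatous polyps, or with polyps that have no histology, out of both B and C in the primary analysis, and report them as a separate group. They should not be moved into C, because C is meant to define the normal range in people without bowel pathology. Add a sensitivity analysis that includes them, for example in B, as the present label can be read.

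Histology is already used for allocation, so no new procedure is needed. The cost is a somewhat smaller group B, a slightly wider interval for the adenoma AUC, and one more group to report.

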An actual connection between the proposed screening markers and the detection of colorectal cancer and adenomas would have a significant impact on: a) target population compliance, b) re-definition of the cancer pathway for candidate patients by changing the indications for colonoscopy and c) the cost-effectiveness, vital for patients' survival and the sustainability of the NHS, by means of earlier cancer/adenoma diagnosis.

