2.1 EVIDENCE

2.1.1 Serum neurotensin/IL-8 values in colorectal cancer

Serum neurotensin/IL-8 values in the diagnosis of colorectal cancer have been reported for first time in literature by our own group.[18, 19] This pilot study aimed to determine the feasibility of serum neurotensin/IL-8 values being used as a screening tool for colorectal cancer. Fifty-six patients and 15 healthy controls were assigned to seven groups according to their disease entity based on theater records and histology report. Blood samples for neurotensin and IL-8 were measured using an enzyme-linked immunosorbent assay.

There were no differences in the clinical and biochemical parameters of patients and controls. Group (p= 0.003) and age (p= 0.059: marginally significant) were independent predictors of neurotensin plasma values. Neurotensin (p= 0.004) and IL-8 (p= 0.029) differed between healthy and colorectal cancer patients. Neurotensin values differentiated the control group from all remaining groups.

The value of plasma neurotensin ≤54.47 pg/ml at enrollment selected by ROC curves demonstrated a sensitivity of 77%, specificity of 90%, and an estimate of area under ROC curve (accuracy) of 85% in predicting colorectal cancer.

At enrollment, the value of plasma IL-8 ≥8.83 pg/ml had a sensitivity of 85%, specificity 80%, and an estimate of area under ROC curve (accuracy) of 81% in predicting colorectal cancer.

Our results depicted that IL-8 should be used complementary to neurotensin due to its lower specificity. None of the colorectal cancer patients displayed a combination of high neurotensin and low IL-8 values (beyond cutoffs). Unpredictably, 3 out of 13 patients in the colorectal cancer group had neurotensin values above the cut-off value defined by the ROC curve. Notwithstanding, the IL-8 values of the same patients were high and well above the cut-off value, as our analysis anticipated for this group. Two other colorectal cancer group patients unexpectedly had low IL-8 values, but they also had low neurotensin values, as our analysis expected for this group. None of the colorectal cancer group patients displayed a combination of high neurotensin and low IL-8 values (which would be in contrast with our analysis).

Finally, one healthy control had a low neurotensin value as well as a low IL-8 value.

This pilot study[18] implicated that a blood neurotensin/IL-8 system may be used as a screening tool for colorectal cancer.

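### Both primary ROC analyses use only normal-colonoscopy controls and leave other benign findings without a group, so accuracy may look too favourable for triage of all referred patients

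*Protocol*

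**What the plan says.** Protocol Section 3.1 states that "individuals will be assigned in three groups" on the basis of the colonoscopy and histology results. Group A holds the cancers, group B the adenomas (its label adds the word polyp in brackets), and group C is defined as "No pathology/normal colonoscopy". The section then fixes two primary analyses to set the marker cut-offs, A versus C for cancer and B versus C for adenomas. Its reason for using participants without bowel pathology is to establish normal values of the two markers. Section 3.3 makes the ROC-selected cut-offs and the AUC the primary endpoints.

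Section 3.2 enrols people over 50 referred for colonoscopy whatever the indication. The only benign bowel disease among its exclusions is inflammatory bowel disease.

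On intended use, Section 1.8 expects the markers to redefine the patient pathway by "changing the indications for colonoscopy". Section 2.1.1 sets out the rule: low neurotensin leads to colonoscopy, and so does high neurotensin with high IL-8. The same section says of the pilot, which had seven groups: "Neurotensin values differentiated the control group from all remaining groups".

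**The concern.** A triage rule is applied before anyone knows what the colonoscopy will show. The people it must sort include those with adenomas, those with other benign disease and those with a normal bowel. Specificity and AUC measured against the last of these describe the easiest comparison.

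If people with non-cancer findings test positive more often than people with a normal bowel, leaving them out raises apparent specificity and AUC, and the chosen cut-off is tuned to a contrast that will not be met in practice. The affected quantities are the primary endpoints themselves. A separate practical gap is that a participant with, say, diverticular disease is enrolled and bled, yet the protocol does not say where that person is analysed.

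**Working it through.** **Who is in each contrast**

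- Cancer contrast: A and C. Group B is in neither arm.
- Adenoma contrast: B and C. Group A is in neither arm.
- Other benign findings: not cancer, not adenoma, and not a normal colonoscopy, so no group is stated.
- Other analyses: Section 4.1 describes ROC curves for cancer and for adenomas without naming a different control set. The secondary comparison with the two-week referral and FOB pathway (Sections 3.1 and 4.2) does not state its control set. No section gives cancer versus all non-cancer.

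**The protocol's own sample size**

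Inputs from Section 3.5: AUC 0.85, 95% interval of full width 0.1, binormal ROC, adenoma/cancer prevalence 20-30%.

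Formulas: A = 1.414 × z(0.85) = 1.4655; k = (1 − prevalence)/prevalence; V = 0.0099 × exp(−A²/2) × [(5A² + 8) + (A² + 8)/k]; cases = 1.96² × V/0.05²; N = cases × (1 + k).

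- 20% prevalence (k = 4): 110.6 cases, N = 552.9. The protocol states 553.
- 30% prevalence (k = 2.333): 120.0 cases, N = 400.0. The protocol states 400.

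Both reproduce. The calculation counts every participant as either a case or a control, whereas the Section 3.1 contrasts do not use everyone.

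**Illustrative size**

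From the protocol: 500 participants (Section 1.5), cancer yield 4% (Section 1.8), adenoma/cancer 20-30% (Section 3.5). Applying the 4% to this cohort is an assumption. It gives 20 cancers, 480 non-cancers, and adenomas in 16-26% of participants (80 to 130).

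Assumed, with no source in the protocol:

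- f = 20-45% of non-cancer participants have an adenoma or other finding.
- Their marker is shifted 0.5-1.0 SD towards the cancer range.
- The cut-off has 90% specificity in group C, as the pilot reported for neurotensin (Section 2.1.1).

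Specificity in the shifted participants is Φ(1.2816 − shift), which is 0.783 at 0.5 SD and 0.611 at 1.0 SD.

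*Cancer-only target* (all 480 non-cancers as comparator):

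- f = 0.20, 0.5 SD: 0.80 × 0.90 + 0.20 × 0.783 = 0.877, about 59 false positives.
- f = 0.45, 1.0 SD: 0.55 × 0.90 + 0.45 × 0.611 = 0.770, about 110 false positives.
- At 90% specificity there would be 48, so the excess is about 11 to 62.

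*Cancer-or-adenoma target* (adenomas removed from the comparator):

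- f = 0.20 with 80 adenomas: 96 − 80 = 16 others among 400. At 0.5 SD, (384 × 0.90 + 16 × 0.783)/400 = 0.895, about 2 extra false positives.
- f = 0.45 with 130 adenomas: 216 − 130 = 86 others among 350. At 1.0 SD, (264 × 0.90 + 86 × 0.611)/350 = 0.829, about 25 extra.
- f = 0.45 with only 80 adenomas: 216 − 80 = 136 others among 400. At 1.0 SD, (264 × 0.90 + 136 × 0.611)/400 = 0.802, about 39 extra.
- f = 0.20 cannot occur with 130 adenomas, since 96 is less than 130.

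The loss is zero if participants with non-cancer findings test positive exactly as often as normals.

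**Does a wider comparator cost precision?**

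With the same variance formula, AUC 0.85 and 20 cancers, the 95% interval width is 0.224 against 400 normals and 0.223 against all 480 non-cancers.

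**The case against.** The strongest reply is that the control choice is deliberate and suits an early study. Section 3.1 gives a reason for it, Section 2 calls the work a pilot, Section 3 says results will not affect participants' care, and Section 5.5 plans a multicentre study if results are promising. Contrasts of diseased with normal participants are common at that stage. This justifies having group C and keeping its contrasts. It does not justify making C the sole comparator for cut-offs and AUC meant to change who is sent for colonoscopy.

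Four stronger readings are tempting, and the protocol does not support them.

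- *Adenomas are false positives.* The title and Sections 1.8 and 2 make adenomas a detection target, so sending an adenoma patient to colonoscopy is a success under the combined aim. They count as false positives only for the separate cancer cut-off.
- *The pilot proves the bias.* Section 2.1.1 gives neither direction nor size for the non-cancer disease groups. Those groups were formed from theatre records and histology, so the fact that 43 of the 56 patients (56 − 13) did not have colorectal cancer says little about the case-mix of colonoscopy referrals. The statement makes the bias plausible and no more.
- *Every benign finding is dropped.* Group B's label mentions polyps, so a non-adenomatous polyp may belong there, and inflammatory bowel disease is an exclusion. Section 3.1 may intend to allocate everyone. Diverticular disease and similar findings remain undefined; that they leave both analyses is an inference.
- *The sample size is wrong.* Its arithmetic is right on its own inputs, and changing the comparator barely alters precision for the cancer AUC.

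**Conclusion.** The structural point holds: both primary contrasts use normal-colonoscopy controls, adenomas are outside the cancer contrast, and some enrolled participants have no stated group. Upward bias in specificity and AUC for the intended use is likely but not demonstrated. It requires people with non-cancer findings to test positive more often than normals.

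The numerical results are illustrations resting on the assumed proportions and shifts, not estimates. The cancer-only range of 77-88% is the larger effect. The 83-90% range for the combined target pairs the low proportion of findings with the low adenoma prevalence and the high with the high; the mixed pairing extends it to 80%. Confidence is high in the structural point and limited in the size.

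**What to change.** In Section 3.1, add a group D for any other colonoscopic or histological finding, and state whether non-adenomatous polyps belong to D or to B.

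Estimate cut-offs, AUC and specificity in the full enrolled cohort as A versus B+C+D (cancer) and A+B versus C+D (cancer or adenoma), and base any triage conclusion on these two contrasts. Keep A versus C and B versus C, labelled as normal-range analyses. Carry the same definitions into Sections 3.3, 4.1 and 4.2, including the control set of the secondary comparison.

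The cost is protocol wording and one extra category on the case form, since colonoscopy and histology results are already obtained. Cancer-AUC precision is essentially unchanged. The real downside is that reported specificity will probably be less favourable.
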